4 STUDY PROCEDURES

4.1 Screening & Enrollment

The protocol for the recruitment, consent, and retention of participants will be identical in all practices. As part of the clinical workflow, all parents in control and intervention practices will be asked about their individual smoking status on the iEHR pre-visit screening questionnaire (Appendix 5 for intervention practices and Appendix 5A for control practices). We will deploy several strategies to maximize screening and enrollment efforts.

The study team/CHOP Clinical Reporting Unit (CRU) and/or Research Enhancement Core (REC) will generate rosters of potentially eligible parents for the upcoming visit. Rosters will include all upcoming visits at study practices of parents who answered, “yes” to either of the screening questions: *“Have you smoked a cigarette, even a puff, in the past 7 days?” and “Have you smoked any other tobacco product (cigars like black and mild, hookah), even a puff, in the past 7 days?”* on the iEHR pre-visit screening questionnaire. The study team will offer enrollment into the study to these potentially eligible parents in-person at the primary care site, via the phone or e-mail.

Additionally, at participating CHOP primary care sites, study team will also review the medical records to identify parents who self-reported as smokers (answered “yes” to either of the screening questions: *“Have you smoked a cigarette, even a puff, in the past 7 days?” and “Have you smoked any other tobacco product (cigars like black and mild, hookah), even a puff, in the past 7 days?”* on the iEHR pre-visit screening questionnaire. (Appendix 5 for intervention practices and Appendix 5A for control practices) to approach them and offer enrollment in the study longitudinal cohort. If a parent is not interested in participating in the study, the research team will document this information in REDCap (child’s name, MRN, parent’s relationship to the child, practice name and date of the visit).

Potentially eligible families who are missed in the CHOP primary care sites will also be reached via recruitment emails, text messages and calls facilitated by the study team and/or CHOP Research Enhancement Core (REC). All outreach methods (e-mail, texts, calls) will include information about how parents can opt out from being contacted about this study in the future.

Smoking parents will be recruited in one of these ways:

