- 1. In-office enrollment:** At participating CHOP primary care sites, study team will approach eligible parents i.e. those who self-reported as smokers (answered “yes” to either of the screening questions: *“Have you smoked a cigarette, even a puff, in the past 7 days?” and “Have you smoked any other tobacco product (cigars like black and mild, hookah), even a puff, in the past 7 days?”* on the iEHR pre-visit screening questionnaire (Appendix 5 for intervention practices and Appendix 5A for control practices) to approach them and offer enrollment in the study longitudinal cohort. Study team will confirm eligibility criteria using Eligibility Form (Appendix 10) prior to consent and enrollment. If a parent agrees, they will be consented using Informed Consent of Parent (Appendix 3b and 3bE (for intervention group) and 3 and 3E (for control group)). After consent, parents in the intervention arm will also be offered the additional support of CHOP CHNs (Attachment 11) (see section 4.2.2. Community Health Navigators for more detail). Parent Enrollment Survey (Appendix 4) will be then administered by the RA in both intervention and control

practices. The Parent Enrollment Survey (Appendix 4) includes additional questions assessing parental vaping status, stage of readiness to change, demographic information, tobacco related attitudes and behaviors and parents' contact information (~ 15 minutes).

In-office enrollment for parents that don't complete the iEHR pre-visit screening questionnaire: At participating CHOP primary care practices, screening questionnaires are assigned to a patient record as opposed to each parent and that sometimes results only in one parent being screened for smoking as opposed to each parent. The study team will fill these gaps by offering enrollment into the study for every smoking parent or legal guardian present at the visit.

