2. **Hybrid enrollment from in-office to remote:** If during the office visit, the parent who was screened positive for smoking and eligible for the study (answered "yes" to either of the screening questions: *"Have you smoked a cigarette, even a puff, in the past 7 days?" and "Have you smoked any other tobacco product (cigars like black and mild, hookah), even a puff, in the past 7 days?"* on the iEHR pre-visit screening questionnaire (Appendix 5 for intervention practices and Appendix 5A for control practices) doesn't have time to complete enrollment or prefers to complete enrollment at home, the study team will ask the parent if he/she is interested in remote enrollment and will ask to collect their contact information for remote enrollment.

Hybrid enrollment if consented in office: If the eligible participant's consent was completed during the visit but the participant doesn't have time to complete the enrollment survey, we will follow up with them remotely to complete the survey or complete the survey during a future visit to the participating office.

All contact information will be stored and shared in a secure HIPAA compliant way (i.e., using CHOP OneDrive). The study team will then attempt to follow up with the parent(s) and conduct enrollment remotely.

3. **Remote enrollment:** We will also deploy additional recruitment approaches, including calling, emailing and texting eligible participants (those who answered "yes" to either of the screening questions: *"Have you smoked a cigarette, even a puff, in the past 7 days?" and "Have you smoked any other tobacco product (cigars like black and mild, hookah), even a puff, in the past 7 days?"*) on the iEHR pre-visit screening questionnaire at the study practices. The roster of eligible participants will

be generated by the study team and/or CHOP REC. Parents that were already enrolled in the study will be excluded.

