For outreach calls, the study team will briefly explain the purpose of the call and introduce the study prior to consent. If the parent agrees to participate, the consent and survey will be sent to them electronically via text or e-mail. During the phone outreach, parents will not be texted or e-mailed the study materials without verbally agreeing to it during the call. All outreach emails and texts will contain the REDCap link inviting them to consider participation in the study. Parents who choose to participate will be screened for eligibility via the REDCap survey (Eligibility Form - Appendix 10) and they will provide informed consent/HIPAA authorization electronically (Appendix 3bE (for intervention group) and 3E (for control group). After they electronically sign the consent, parents in the intervention arm will also be offered the additional support of CHOP CHNs (Attachment 11) (see section 4. 2.2. Community Health Navigators for more detail). Then parents in both intervention and control groups can complete the enrollment form (Appendix 4) either at home themselves or while having a research assistant on the call. If the parent picks up the call but it's not a good a time for them to complete the enrollment, the RA may offer them an option to receive follow up with the RA via text to set up the best time for the enrollment call. The research presents minimal risk to participants and involves no procedures for which written consent is normally required outside of the research context.

If the parent has a working e-mail address on record, we may also attempt to outreach to them via e-mail (e-mail template: Appendix 12 for intervention and Appendix 13 for control). E-mail letters may be customized for each practice based on the input from practice physicians and staff. E-mail letters will include an option to opt-out from further communication and will notify the parents that if they do not enroll into the study or opt out, within 2 weeks we may follow up with them via phone call or text. Follow up texts (with up to 3 reminders if the parent doesn't opt out) will include a brief information about RAs call back number to learn more about the study. Parents may opt out at any time.

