4.3 Follow-up

4.3.1 Parent Follow-up

For smoking parents in the longitudinal cohort (See Figure 1), 12-month follow-up in-person/remote survey (Appendix 6), and biochemical validation of self-reported 7-day abstinence will be obtained using proven protocols to collect the samples in-person at the practice or by using remote survey and mail-in cotinine swabs for parents not present at the practice.

- Cotinine levels will be measured for all parents who reported quitting smoking
- In addition to the cotinine test, parents who report current use of NRT or e-cigarettes or have cotinine levels ≥ 10 ng/ml will have the option to get carbon monoxide levels tested to confirm combusted tobacco abstinence.
 - For in-office follow ups (see below for more details), to prevent missing parents who might be eligible for carbon monoxide test, we may ask parents who report current use of NRT or e-cigarettes to get their carbon monoxide levels tested in-office without knowing their cotinine levels yet. We will use their carbon monoxide test readings only if their cotinine levels are ≥ 10 ng/ml (we will get the cotinine results from the lab).

The enrolled parent will be eligible for the 12-month follow-up, about three-weeks before their 12-month study enrollment date. We will deploy several strategies to maximize follow-up efforts.

We will generate rosters of enrolled parents due for their 12-month follow up, who have an upcoming visit scheduled during the follow-up window. These reports will be regularly updated to reflect newly scheduled appointments.

Enrolled parents eligible for follow-up will complete the follow-up assessment in one of the following three ways:

1. **Follow-up via text/email/portal message(myCHOP):** Parents who consented to texting on the baseline Parent Enrollment Survey (Appendix 4) may be texted a follow up survey link. Participants may receive several text reminders to remind the parent to complete the follow up survey. Parents may also be sent the follow up survey link by email or through portal messaging (myCHOP).

If the parent completes the survey via text, email, or myCHOP, and is eligible for the cotinine swabs and CO test, the last page of the survey will notify them that they

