In our intention-to-treat analysis, all participants lost to follow-up will be considered smokers. We will also use multiple imputation techniques, as appropriate to impute missing data. We will use generalized linear mixed-effects models (Gaussian, logistic, or Poisson, as appropriate) to compare the primary outcome between arms. To the extent allowed by the sample, we will build a logistic regression model that includes potential confounding factors, particularly those that are unbalanced between iEHR+Navigator vs usual care control groups to compare the parental 7-day quit rates. We will attempt to identify predictors of parental quitting to determine whether any of these factors modify intervention effect. To determine whether the intervention effect differs among subgroups, we will test the interaction between intervention group and these predictors. Specifically, to the extent allowed by our sample size, exploratory analyses will compare quit rates in subgroups of smokers characterized by cigarettes per day, e-cigarette use, number of smokers in the home, demographic variables (parent sex, age, race, education, child age) and treatment use. We will conduct a difference in difference analyses from baseline to follow up to evaluate the effect of the intervention on changes in smoking related factors like mean cigarettes per day and daily smoking rates.

Secondary outcomes

1. Rates of smokefree homes and cars, use of NRT and duration of use, and quitline enrollment, as assessed by validated surveys of parents, will be compared between iEHR+Navigator and usual care control arms. Change in parental smoking inside homes and cars, use of NRT, and receiving services from cessation programs will be based on the baseline and 12-months enrollment visit, comparing change from baseline to 12 months between intervention groups and usual care control practices. We will follow a similar analysis strategy to that stated above in primary outcome analysis.

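### The adjusted quit-rate model picks covariates by observed imbalance, and treatment use, a consequence of arm, is a planned effect-modification subgroup; a minor related point is that the baseline survey follows intervention offers

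*SAP*

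**What the plan says.** **Adjusted model and subgroups (SAP, Primary outcome).** The first analysis named is a generalized linear mixed model comparing arms. The SAP then adds, sample permitting, a logistic model with potential confounders and gives particular weight to those out of balance between arms. It gives no list and no rule for judging imbalance. It plans interaction tests and exploratory subgroups defined by cigarettes per day, e-cigarette use, number of smokers in the home, parent sex, age, race and education, child age and, last, treatment use. Treatment use is given no definition or time point.

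**Change from baseline (SAP, Secondary outcomes, item 1).** Rates of smoke-free homes and cars, NRT use and quitline enrolment are compared between arms. The same item then plans a second analysis of home and car smoking, NRT use and cessation services, "comparing change from baseline to 12 months between intervention groups and usual care control practices". It does not say which of the two is the main analysis.

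**What baseline is.** Protocol 4.3.1 treats the enrolment survey as the baseline survey: "Parents who consented to texting on the baseline Parent Enrollment Survey (Appendix 4) may be texted a follow up survey link". Protocol 9.7.1 also places it at baseline.

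**Order of steps (Protocol 4.1).** In the office: "After consent, parents in the intervention arm will also be offered the additional support of CHOP CHNs"; the survey comes next: "Parent Enrollment Survey (Appendix 4) will be then administered by the RA in both intervention and control" practices. Remotely: "After they electronically sign the consent, parents in the intervention arm will also be offered the additional support of CHOP CHNs"; and after that, "Then parents in both intervention and control groups can complete the enrollment form (Appendix 4"). For parents who consent in the office but run out of time, "we will follow up with them remotely to complete the survey or complete the survey during a future visit to the participating office". In addition, "Potentially eligible families who are missed in the CHOP primary care sites will also be reached via recruitment emails, text messages and calls".

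**The concern.** A covariate that is out of balance by chance need not predict quitting, and one that predicts quitting need not be out of balance. If the list is settled after imbalance has been seen, different samples give different models, and a reader cannot tell the planned adjusted result from one chosen among several.

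Treatment use is a different kind of problem. Practices are randomised before parents enrol, and the intervention acts directly on prescriptions and referrals. Parents who use treatment in the intervention arm are not the counterparts of those who use it under usual care. An interaction with treatment use therefore does not estimate how the effect varies across kinds of parent, and the control side of the user subgroup may be nearly empty.

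On the survey, a change score subtracts whatever arm difference exists when baseline is taken. If part of that difference is early response to the offers, part of the effect is removed.

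**Working it through.** **1. The plan's own figure.** Inputs from Protocol 6.4: quit rates 13.8% and 7%, ICC .014, 400 per arm, 4 practices × 5 clinicians, hence 400/20 = 20 parents per clinician. Two-sided 5% is assumed, as no alpha is stated.
- Design effect 1 + (20 − 1) × .014 = 1.266; effective n = 400/1.266 = 316.0 per arm; power 80.1%. The stated 80% is reproduced.
- With the same ICC applied to practices of 100: 1 + 99 × .014 = 2.386; effective n = 167.6; power 53%. That is a separate matter. It is used here only as the other end of a range.

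**2. Chance imbalance (illustration; assumes the quit-rate ICC also holds for baseline variables).** The 95% range of an arm difference is ±1.96 × √(2p(1 − p)/n_eff).
- 20 per cluster: ±4.7 points at p = 10%, ±7.8 at p = 50%.
- 100 per cluster: ±6.4 and ±10.7.

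Visible imbalance is therefore to be expected without any fault in the allocation.

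**3. How often a covariate would be flagged (illustration).** Suppose imbalance were judged by independent 5% tests on the eight factors that precede treatment use in the SAP's subgroup list. The SAP names no test and lists these as subgroup factors, not covariates.
- Tests that allow for clustering: 1 − 0.95^8 = 34% chance of at least one flag.
- Tests that ignore it: the per-test rate is 2 × (1 − Φ(1.96/√DEFF)) = 0.082 (20 per cluster) or 0.204 (100 per cluster), giving 1 − (1 − r)^8 = 49% or 84%.

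**4. Treatment-use subgroup (illustration).** Earlier-trial figures in Protocol 1.1 and 1.3, applied to 400 per arm:
- Prescription 34% v 0%: 136 v 0. Quitline referral 25% v 0%: 100 v 0.
- NRT 38% v <1%: 152 v fewer than 4. Quitline 32% v <1%: 128 v fewer than 4.
- Two-year figures, 10% and 7% v 0%: 40 and 28 v 0.

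These are delivery or enrolment rates, not use. Parents who buy NRT themselves would add some control users.

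**5. Survey order.** Set side by side, the sections show:
- The navigator offer precedes the survey on both routes that are spelled out (4.1).
- For screened parents, the Quitline and SmokefreeTXT offer sits inside the screener, which comes earlier (4.2.1). The timing of the automatic NRT prescription relative to the survey is not stated.
- First navigator contact is about a week after enrolment (4.2.2), so a same-day survey leaves little time to respond. Delayed surveys are the likelier route.
- No limit on the time from visit to survey is stated. The two-week interval in the remote-enrolment text runs from the recruitment e-mail.

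Let D be the true 12-month difference, f the share of intervention-arm surveys late enough to capture a response, and u the early arm difference among them. The change estimate is D − f × u. Neither f nor u is given. Assume f = 0, 10% or 25%, and u from 8.3 points (Quitline gain from electronic over paper referral, 1.3) to 34 points (prescription delivery, 1.3):
- f = 0: no loss.
- f = 10%: 0.10 × 8.3 = 0.8 to 0.10 × 34 = 3.4 points.
- f = 25%: 0.25 × 8.3 = 2.1 to 0.25 × 34 = 8.5 points.

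A loss of 3.4 points would be 34%, 17% or 11% of an assumed true difference of 10, 20 or 30 points. Both values of u are poor proxies: one compares two forms of referral, and the other counts every prescription delivered as NRT use already reported at baseline.

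**The case against.** Much can be said for the plan. The mixed-model comparison comes first, the adjusted model is supplementary, and imbalance is the leading rule but not the only one. The statisticians are blinded to which label is the intervention (Protocol 3.2, 9.1.2), which limits deliberate steering. The subgroups are labelled exploratory and depend on sample size. All of this stands and lowers the weight of the point. None of it supplies a covariate list or makes treatment use a baseline characteristic.

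On the survey the objection is stronger. A reader might infer that the secondary results are materially diluted. The documents do not support that. Whether early response reaches the baseline value depends on the items and recall period in Appendix 4, which is listed but not in the documents. Direct 12-month comparisons are already planned (SAP Secondary outcomes 1 and 3; Protocol 6.2), and Table 3 defines pharmacotherapy use as use since the pediatric visit, which has no natural baseline value. Protocol 6.3.1 gives a general source for baseline smoking data: the screener for smoking status and the enrolment survey for tobacco-related behaviours. Moving the survey ahead of the navigator offer would also leave screener and NRT offers in place and would not shorten delayed surveys. Positive screeners are re-prompted every three months if they have a visit (3.4.2), so some parents may have met the offers before. What remains is a question of order and priority, not a bias of known size.

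**Conclusion.** Two faults in the stated analysis stand: covariate selection led by observed imbalance, and treatment use as an effect modifier. Both follow from the SAP text and need no assumption about size. The survey-order point also stands, but as minor: change scores for NRT use and cessation services could be pulled toward no effect by an unknown amount that may be zero. Early response cannot by itself create a false positive.

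A reader might also infer that the primary result is compromised. It is not: the main mixed-model comparison of confirmed quitting uses neither a change score nor the imbalance-chosen covariates. The flag rates of 34%, 49% and 84%, the subgroup counts and the dilution points are illustrations under the assumptions given, not properties of the plan. Overall the point is minor to moderate and confined to adjusted, exploratory and secondary analyses.

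**What to change.** 1. **Covariates.** Replace imbalance-led selection with a fixed list used whatever the imbalance: the matching factors (practice size, Medicaid rate) as far as the number of practices allows, plus baseline variables the intervention cannot alter, such as parent age, sex and education and child age.
2. **Treatment use.** Remove it from the interaction and subgroup list and report it descriptively by arm.
3. **Secondary outcome 1.** Name the direct 12-month between-arm comparison as the main analysis for NRT use and cessation services, in line with Table 3, with change scores supportive.
4. **Survey.** Give it right after consent and before the navigator offer on every route. Record the visit-to-survey interval and report it by arm.

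Items 1 to 3 are SAP text only and remain possible after enrolment has begun. Item 4 swaps two enrolment steps and adds one reported interval; it removes only the navigator offer from the period before the survey. The price is some loss of protection against chance imbalance when change scores become supportive, which matters with as few as eight practices.

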3.3.2 Total Number of Study Sites/Total Number of Subjects Projected

The study will be conducted at a minimum of 8 primary care sites at CHOP with approximately 40 clinicians participating across these 8 sites, and proportionally more clinicians if other sites are added.

Our goal is to stop recruitment when 400 parent subjects are enrolled per arm in the longitudinal cohort (800 across both arms). The study has been designed to achieve this goal by recruiting 100 parents from each of four sites per arm, and for this situation we will have 80% power for the primary outcome (iEHR + Navigator vs. usual care control), for a clinically meaningful difference in smoking cessation rates. If some practices accrue subjects at a rate which makes it unlikely that these practices can achieve the recruitment goal of 100 subjects, then we will estimate the likely shortfall, and increase the recruitment goals in faster-accruing practices in order to attempt to preserve statistical power. We may also add additional practices to maximize the likelihood of meeting the recruitment goal of at least 400 parents enrolled in each arm. If we add practices, we will do so in pairs, matched by practice size and Medicaid rate, and randomly assigned to the control and intervention groups. If the study must be terminated before the recruitment goal, this termination will be made exclusively for reasons (such as time and budget) which are unrelated to study outcomes.

In the intervention practices, a minimum of one clinician and one key staff will complete an in-depth qualitative interviews 6-weeks following implementation and after 12, and 24 months.

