Using the workflows outlined above, we will continue to enroll parents until approximately 400 parents have been enrolled in each arm. If some practices accrue subjects at a rate which makes it unlikely that these practices can achieve the recruitment goal of 100 subjects, then we will estimate the likely shortfall, and increase the recruitment goals in faster-accruing practices in order to attempt to preserve statistical power. We may also add additional practices in one or both arms to meet the recruitment goal of 400 parents enrolled in each arm. A notice to parents

may be posted where all can see it when entering/registering for their pediatric visit. The notice may announce that the practice is participating in a research study and that parents/guardians may be approached by a study RA during their office visit. Parent screening and enrollment procedures may be modified to kiosk/telephone/remote screening and enrollment due to procedures that may be in place at CHOP to protect people from COVID-19 risks.

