4.2.2 Community Health Navigators (CHNs)

Table 2. Community Health Navigator role

CHN session	Ask ²⁵ (Assessment)	Assist (Counseling)	Assist (Care coordination)	Refer (Resources)
1	Identify all household tobacco users 
 • Readiness to quit • Smoke-free home & car rules • Previous quit attempts • NRT insurance coverage • Identify pharmacy 	Enhance intervention content: 
 • Quit smoking tools & techniques for all tobacco users • Thirdhand smoke • Set quit date 	
 • Ensure connection to Quitline • Ensure NRT access at local pharmacy • Communicate with child's clinician & if possible, parents' clinician about household smoking status using iEHR 	Follow-up to ensure resource awareness & receipt of: 
 • NRT scripts • Quitline • SmokefreeTXT
2	
 • Reassess motivation and progress • NRT script filled • Connected with Quitline/ local cessation resources • Assess smoke-free zones 	Reinforce intervention content and all of the above	
 • All of the above 	
 • Develop strategies to overcome barriers to service receipt

Parents in the intervention arm will also be offered the additional support of CHOP CHNs (Appendix 11). CHNs are employees of CHOP Community Asthma Prevention Program (CAAP) led by the co-PI of this study [name]. CHNs are listed on the CHOP study team and when additional CHOP CHNs are hired for this study, they will be added to the study team. CHNs will work with offices to provide customized smoking cessation support to household tobacco users through phone follow-up, ensuring access to medications and services, and/or home visits, depending on the needs of each family and as study resources allow (Table 2). Home visits could be virtual if there are in-person visit restrictions due to COVID-19.

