6.4 Sample Size and Power

Sample size calculations are based on having at least 8 practices with a minimum of 5 clinicians per practice. Clinically important and conservative estimates of validated 12-month quit rates based on prior studies are 13.8% in the iEHR + Navigator group and 7% in the usual care control group. These estimates are based on the worst-case scenario from prior studies where all enrolled parents lost to follow-up were assumed to be smokers at 12-month follow-up. The effective sample size needed for the primary outcome accounts for clustering at the clinician and practice level (4 practices per arm x 5 clinicians per practice) with intra-class correlation of .014 calculated from our previous research. By enrolling approximately 100 parents in each practice (400 per arm), we will have 80% power for the primary outcome (iEHR + Navigator vs. usual care control). Effect sizes for outcomes other

than cessation will likely be much greater; the study will have adequate power to detect these differences, shown in our prior studies.

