2. Establish the incremental cost per quit of intervention. The healthcare system's perspective is central to establishing the interventions' disseminability and sustainability. As a secondary analysis, we will consider costs from a societal perspective to pave the way for future cost-utility analyses. We will calculate the incremental cost per quit of the iEHR+Navigator intervention relative to usual care, as we have done in prior studies: $(\text{Total cost at 12 months}_{\text{arm[i]}} - \text{Total costs}_{\text{arm[j]}}) / (\text{Total biochemically confirmed quits at 12 months}_{\text{arm[i]}} - \text{Total biochemically confirmed quits at 12 months}_{\text{arm[j]}})$. Development costs for iEHR will not be included in primary analyses as the iEHR will be fully developed and ready for dissemination by the time the intervention begins. Direct costs include iEHR set-up, customizing, implementing, and sustaining the systems changes that support service delivery and cessation, electronic tablets, and related clinician work. Direct costs further include: the CEASE intervention staff time to support the practice leader and the time clinicians and office staff take to learn and use the online module. Time use will be tracked by administrative records, direct observation by the RA, and surveys. For the iEHR+Navigator arm, we will create a log to note the types of CHN outreach efforts, time spent, and the type of services delivered to smoking parents. Personnel costs will reflect national average wages for each personnel type. We will use Monte Carlo simulation methods to develop confidence bounds on our cost-per-quit estimates. Following standard methods of economic evaluation in prior studies, we will also perform parameter-specific sensitivity analyses in which individual parameters are varied singly and in combination, through plausible ranges to assess the relative impact different elements of the program have on overall cost-effectiveness.

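### The cost-per-quit formula subtracts arm totals, so unequal enrolment moves the ratio and yields incremental quits even with no effect; the shift is small near 400:400 and grows with imbalance

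*SAP*

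**What the plan says.** The SAP (Secondary outcomes, item 2) gives the formula. The numerator is the intervention arm's total cost at 12 months minus the usual care arm's total cost; only the first cost term carries the time point. The denominator is the difference between arms in "Total biochemically confirmed quits at 12 months". Both are arm totals. Protocol 5.2 (Table 3) and 6.2 name the outcome but give no other formula.

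Equal arms are a target. Protocol 4.1 says "we will continue to enroll parents until approximately 400 parents have been enrolled in each arm", and Protocol 3.3.2 says "Our goal is to stop recruitment when 400 parent subjects are enrolled per arm in the longitudinal cohort". The same section provides for ending early, for reasons such as time and budget: "If the study must be terminated before the recruitment goal".

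Three other statements bear on the calculation:

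- Protocol 6.4 plans for quit rates of "13.8% in the iEHR + Navigator group and 7% in the usual care control group".
- For the primary analysis the SAP states that "all participants lost to follow-up will be considered smokers", so an arm's quit count is its enrolled number times its quit proportion.
- On costs, the SAP states: "Direct costs include iEHR set-up, customizing, implementing, and sustaining the systems changes that support service delivery and cessation". Several of these are incurred by the practice and not by each parent.

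**The concern.** An incremental cost-effectiveness ratio compares what one more quit costs when the same population receives one strategy or the other. Differences in arm totals measure that only if the two arms contain the same number of parents. Otherwise part of each difference reflects how many parents were enrolled. A larger intervention arm collects more quits and more cost without working any better, and a smaller one does the reverse.

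Incremental cost per quit is a named secondary objective, and the SAP ties it to whether the programme can be disseminated and sustained. The SAP plans Monte Carlo bounds, but bounds drawn around the same unscaled ratio would carry the same shift. The primary outcome is a quit rate, so the plan also measures effect on two different scales.

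**Working it through.** **Inputs.** Quit rates of 13.8% and 7%, 400 parents per arm, an intra-class correlation of 0.014, and 4 practices of 5 clinicians per arm all come from Protocol 6.4. The documents give no costs. I assume 300 per intervention parent and 50 per control parent, and vary the control cost from 0 to 100. The unequal splits are illustrative.

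**The plan's own figure.** With 20 parents per clinician the design effect is 1 + 19 × 0.014 = 1.266, so the effective sample is 400 / 1.266 = 316 per arm. At a two-sided 5% level (assumed; none is stated) power is 80.1%, which matches the stated 80%. I use this design effect below to gauge chance variation.

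**Formulas.** Let n1, c1, p1 be the number enrolled, mean cost and quit proportion in the intervention arm, and n0, c0, p0 those in control.

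- As written: (n1·c1 − n0·c0) / (n1·p1 − n0·p0)
- Per parent: (c1 − c0) / (p1 − p0) = 250 / 0.068 = 3,676

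The two agree when n1 = n0. They also agree at any split if cost per quit is the same in both arms, here at c0 = 300 × 0.07 / 0.138 = 152.

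| n1:n0 | Formula as written | Divided by 3,676 | Same quotient, control cost 0 to 100 |
|---|---|---|---|
| 405:395 | 101,750 / 28.24 = 3,603 | 0.98 | 0.98–0.99 |
| 395:405 | 98,250 / 26.16 = 3,756 | 1.02 | 1.01–1.03 |
| 410:390 | 103,500 / 29.28 = 3,535 | 0.96 | 0.95–0.98 |
| 390:410 | 96,500 / 25.12 = 3,842 | 1.04 | 1.03–1.06 |
| 420:380 | 107,000 / 31.36 = 3,412 | 0.93 | 0.91–0.95 |
| 380:420 | 93,000 / 23.04 = 4,036 | 1.10 | 1.06–1.12 |
| 440:360 | 114,000 / 35.52 = 3,209 | 0.87 | 0.84–0.92 |
| 360:440 | 86,000 / 18.88 = 4,555 | 1.24 | 1.15–1.30 |

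In the last column, each control cost is compared with its own per-parent ratio. The shift is larger when the intervention arm is the smaller one.

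**No effect.** This part needs no cost assumption. If both arms quit at the same rate p, the expected denominator is p × (n1 − n0). At p = 10% that is 1 quit at 405:395, 2 at 410:390 and 4 at 420:380.

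**Scale against chance.**

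- With no effect and 10% quitting in both arms, the SD of the quit difference at 400:400 is √(1.266 × 2 × 400 × 0.1 × 0.9) = 9.5 quits.
- At the planned rates, the standard error of the difference in proportions is √(1.266 × (0.138 × 0.862 + 0.07 × 0.93) / 400) = 0.0241. The 95% range is 0.0207 to 0.1153.
- With incremental cost held constant, cost per quit then runs from 0.068 / 0.1153 = 0.59 to 0.068 / 0.0207 = 3.3 times the point estimate.

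**The case against.** The strongest reply is that the design aims at exactly the condition under which the formula is right. Recruitment is meant to stop near 400 in each arm, shortfalls are met by raising goals in faster practices, and Protocol 3.3.2 adds practices in matched pairs. Protocol 4.1 speaks of adding them in one or both arms, but in order to reach 400 in each, which would restore balance. If one arm stops at 400, the 440:360 shift needs about 400 × 360 / 440 = 327 in the other, a shortfall of 73 in one arm only. This stands: the large splits show how the shift grows and are not predictions.

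The shift is also small beside chance, and more so if the practice is taken as the cluster. With 100 parents per practice and the same correlation (an assumption), the design effect is 1 + 99 × 0.014 = 2.386, the 95% range for the quit difference is 0.003 to 0.133, and cost per quit spans about 0.51 to 22 times the estimate. This stands too. It lowers the priority, but chance error does not excuse a systematic shift that wording can remove.

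The percentages rest on assumed costs, and even their direction does. Above a control cost of about 152 it reverses: at 200, 420:380 gives 1.08 and 380:420 gives 0.89. The dependence on arm size remains either way, and the result under no effect uses no costs.

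The SAP cites prior studies for its method and does not describe the simulation, so a common-size model may be intended. The documents cannot settle that, and the formula they print is unscaled.

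**Conclusion.** The formula is wrong as written, with a small effect close to balance. It is exact at 400:400. Under the planned quit rates and costs of 300 and 50, it moves by about 2% for a gap of 10 parents and 4% for a gap of 20 (1% to 6% across control costs of 0 to 100). At a gap of 80 the shift is 13% downwards or 24% upwards, depending on which arm is larger. The percentages and their direction rest on the assumed costs; the spurious quit difference under no effect rests only on unequal arms. Near the target, the shift is well inside sampling error. The change is still worth making, because the team would otherwise either report a ratio that depends on which arm enrolled more parents, or choose a rescaling after seeing the enrolment figures.

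**What to change.** In the SAP, define incremental cost per quit as the difference in mean 12-month cost per enrolled parent, divided by the difference in 12-month confirmed quit proportion. Use all enrolled parents as the denominator in each arm and count those lost to follow-up as smokers, as in the primary analysis. Rescaling each arm's totals to a common number of parents gives the same result. State the 12-month time point on both cost terms, and base the Monte Carlo bounds on the per-parent ratio.

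The change does not settle fixed practice-level costs. Spread over enrolled parents, a cost incurred only in the intervention arm becomes 400 / 440 = 0.91 or 400 / 360 = 1.11 of its value at 400. If such costs are held fixed while parent-level costs are rescaled, the common-size version no longer equals the per-parent one. The SAP should therefore say how they are allocated. It could also say how navigator time for household members outside the cohort is charged, since Table 2 in Protocol 4.2.2 has the navigator "Identify all household tobacco users"; I have not sized that.

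The cost is SAP wording, including one decision on cost allocation. No new data are needed, and a 400:400 result is unchanged.
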